# 9.2.5 Serious Adverse Events (Including Deaths) and Adverse Events Leading to Study Drug Discontinuation

The number and percentage of subjects experiencing the following categories will be tabulated according to the primary MedDRA SOC and PT. In addition, listing of subjects experiencing the following categories will be generated.

- Treatment-emergent SAEs
- Treatment-emergent AEs leading to discontinuation of study drug
- Treatment-emergent AEs leading to death

## 9.2.6 Adverse Events of Special Interest

Adverse events of special interest will be summarized by SOC and PT and will be based on standardized or company MedDRA queries (SMQs or CMQs), or based on adjudication results.

Detailed information about the search criteria are provided in Appendix A.

## 9.2.7 Post-Treatment Adverse Events

Post-Treatment Adverse Events are defined as AEs starting more than 30 days following discontinuation of study drug in the Treatment Period. The Post-Treatment AEs will be summarized as follows:

- Overview of Post-Treatment AEs
- Post-Treatment AEs by SOC and PT
- Post-Treatment SAEs by SOC and PT

In addition, listing of subjects with Post-Treatment AEs by SOC and PT and Post-Treatment SAEs by SOC and PT will be provided.

#### 9.3 Analysis of Laboratory Data

Data collected from central and local laboratories, including additional laboratory testing due to an SAE, will be used in all analyses, except for Baseline where SAE-related laboratory assessments on or before the first dose of study drug will be excluded. The clinical laboratory tests defined in the protocol operations manual (i.e., hematology and clinical chemistry) will be summarized.

Each laboratory variable will be summarized for all time points (starting with Baseline) with the number of non-missing observations, mean and standard deviation, median, minimum and maximum. For selected laboratory variables including lipid variables, liver variables (alkaline phosphatase, ALT, AST, bilirubin), and hemotological variables (hemoglobin, hematocrit, platelet count, and red blood cell (RBC) count), mean change from baseline to each applicable post-baseline visit will be summarized, with the number of observations, baseline mean, and visit mean. The change from baseline mean, standard error, and 95% confidence interval will be presented for the mean change from baseline within each treatment group and difference between elagolix group and placebo. For lipid variables, in addition to low-density lipoprotein cholesterol (LDL-C), high-density lipoprotein cholesterol (HDL-C), total cholesterol, triglycerides (TG) and apolipoprotein A and B, the following ratios will be included: the ratio of total cholesterol to HDL-C, the ratio of LDL-C to HDL-C, the ratio of TG to HDL-C, and the ratio of non-HDL-C (calculated as total cholesterol minus HDL-C) to HDL-C.

Changes in selected laboratory parameters will be tabulated using shift tables by NCI CTC criteria and categorized as low, normal, or high based on the normal ranges of the laboratory used for each sample. A shift table from baseline either to the worse value (based on NCI CTC criteria) during treatment or to minimum and maximum value (based on normal range), will be created. A similar shift table will be provided to summarize shifts from baseline to the final post-baseline value.

Laboratory abnormalities meeting CTC criteria grade 3 or 4 will be summarized.

The number and percentage of subjects meeting the following sponsor-defined potentially clinically significant lipid values will be summarized at baseline and each relevant visit by treatment group in the appropriate Treatment Period:

- Total cholesterol:  $\leq 300, > 300 \leq 400, > 400 \leq 500$ , and > 500 mg/dL
- HDL-C: < 40 and  $\ge 40$  mg/dL
- LDL-C:  $< 130, \ge 130 < 160, \ge 160 < 190$ , and  $\ge 190 \text{ mg/dL}$
- TG:  $\leq 150, > 150 \leq 300, > 300 \leq 500, > 500 \leq 1000$ , and > 1000 mg/dL
- LDL-C/HDL-C ratio:  $\leq 3$ , and > 3
- Total cholesterol/HDL-C ratio:  $\leq 4.5$ , and > 4.5

In addition, the number and percentage of subjects who have potentially clinically significant (PCS) lipid values meeting the following criteria any time during the appropriate Treatment Period will be summarized by treatment group. Listings will be provided to summarize subject-level laboratory data for subjects meeting PCS criteria.

- Total cholesterol > 200 mg/dL
- LDL-C > 130 mg/dL
- LDL-C > 160 mg/dL
- HDL-C < 40 mg/dL
- TG > 150 mg/dL
- TG/HDL-C ratio > 3.5
- LDL-C/HDL-C ratio > 4

The following plots will be provided by treatment group for HDL-C, LDL-C, and triglycerides during the appropriate Treatment Period:

- Final post-baseline lab values vs. Baseline lab values
- Final post-baseline lab values vs. Baseline lab values for subjects with NCI CTC Grade 3 or 4
- Worst post-baseline lab values vs. Baseline lab values

- Worst post-baseline lab values vs. Baseline lab values for subjects with NCI CTC Grade 3 or 4
- Mean percent change from baseline in lipid parameters over time

In addition, plots of mean lab values over time during the Treatment Period will be provided for hemoglobin, total cholesterol, HDL-C, LDL-C, triglycerides, LDL-C/HDL-C ratio, ALT, AST, bilirubin, apolipoprotein A and apolipoprotein B.

The number and percentage of subjects in each treatment group with maximum on treatment laboratory values meeting the following criteria compared to the upper limit of normal (ULN) during the appropriate Treatment Period will be summarized to assess potential hepatotoxicity.

- ALT  $\ge$  3 × ULN and total bilirubin  $\ge$  2 × ULN
- AST  $\geq$  3 × ULN and total bilirubin  $\geq$  2 × ULN
- ALT and AST  $\geq$  3 × ULN and total bilirubin  $\geq$  2 × ULN
- ALT  $\geq$  3 × ULN and total bilirubin < 2 × ULN
- AST  $\geq$  3 × ULN and total bilirubin < 2 × ULN
- ALT and AST  $\geq$  3 × ULN and total bilirubin < 2 × ULN
- ALT  $\ge$  3 × ULN and total bilirubin  $\ge$  1.5 × ULN
- AST  $\geq$  3 × ULN and total bilirubin  $\geq$  1.5 × ULN
- ALT and AST  $\geq$  3 × ULN and total bilirubin  $\geq$  1.5 × ULN
- $ALT \ge 3 \times ULN, \ge 5 \times ULN, \ge 10 \times ULN, \ge 20 \times ULN$
- $AST \ge 3 \times ULN, \ge 5 \times ULN, \ge 10 \times ULN, \ge 20 \times ULN$
- Total bilirubin  $\geq 1.5 \times ULN$ ,  $\geq 2.0 \times ULN$

The maximum ratio relative to the ULN is used to determine if subjects met the criteria listed above. The ALT, AST, and total bilirubin values do not need to be concurrent in order to meet the defined criteria. For ALT, AST, and total bilirubin, a subject is counted if the post-baseline laboratory value during the Treatment Period meets the above criteria

regardless of Baseline laboratory value (i.e., the post-baseline laboratory value does not need to be worse than Baseline laboratory value).

A listing of all ALT, AST, total bilirubin, and alkaline phosphatase values will be provided for each subject who meets any of the criteria defined above.

The following plots will be generated: peak AST vs. peak bilirubin; peak ALT vs. peak bilirubin.

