#### 5.2.2 Exclusion Criteria

A subject will not be eligible for study participation if she meets any of the following criteria:

- 1. Subject has had menstrual cycles that are > 38 days in length for the past 3 consecutive months prior to Screening.
- 2. Subject has screening pelvic ultrasound or SIS results that show clinically significant gynecological findings such as:
  - A persistent simple ovarian cyst > 5 cm in longest diameter (if the pelvic ultrasounds shows a simple ovarian cysts > 5 cm and  $\le 7$  cm, an ultrasound of

the ovaries may be repeated in approximately 4 - 6 weeks; however, the results must be evaluated prior to Day 1 and not meet exclusion).

- A complex ovarian cyst > 3.5 cm in diameter (longest diameter)
- An endometrioma > 3.5 cm in diameter (longest diameter)
- Large endometrial polyp (≥ 1 cm)
- Intracavitary Submucosal pedunculated fibroid
- 3. Subject had a myomectomy, uterine artery embolization or high intensity focused ultrasound (HIFU) within 6 months prior to Screening.
- 4. Subject had an endometrial ablation within 1 year prior to Screening.
- 5. Subject ≥ 21 years of age at Screening (or age at which Pap smears are routinely performed according to local guidelines) has a Pap smear result that meets exclusionary criteria as indicated in Figure 2, Pap Test Eligibility.
- 6. Subject has active pelvic inflammatory disease (PID).
- 7. Subject's weight exceeds the limit of the DXA machine used for this study.
- 8. Subject's hemoglobin level is < 7 g/dL (subjects with initial screening hemoglobin results < 7 g/dL can be prescribed iron supplements and have their hemoglobin levels retested prior to Day 1).
- 9. Subject had two or more blood transfusions (separate events) within 9 months prior to Screening or required a blood transfusion within 60 days prior to Day 1.
- 10. Subject has clinically significant abnormalities in clinical chemistry, hematology, or urinalysis (excluding findings that are associated with the disease under study such as low hemoglobin or low hematocrit) or a serum creatinine > 2.0 mg/dL at Screening. Clinically significant laboratory abnormalities may be retested prior to Day 1; however the results must meet entry criteria to be eligible for randomization.
- 11. Subject has aspartate aminotransferase (ASAT/SGOT) or alanine aminotransferase  $(ALAT/SGPT) \ge 3.0$  times the upper limit of the reference range or bilirubin

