The laboratory results will be provided by the central laboratory to the investigative site where they will be reviewed, signed and dated by the Investigator. For any value outside of the reference range, the Investigator will review and indicate on the report if the result is clinically significant (CS) or not clinically significant (NCS). The Investigator will evaluate clinically significant laboratory values per standard of care which may include repeating the test to verify the out-of-range value. Clinically significant laboratory abnormalities post randomization may be documented as adverse events, depending on the interpretation of the Investigator (Section 6.0).

All screening laboratory results must be reviewed prior to randomization, including any repeated test results. Screening laboratory tests may be repeated one time prior to Day 1, however, results must satisfy entry criteria prior to randomization. Subjects will not be randomized on Day 1 if Screening laboratory results do not meet entry criteria or are assessed as clinically significant by the Investigator. The laboratory test results obtained from the Day 1 pre-dose samples will serve as the baseline for clinical assessment.

The Investigator will receive Sponsor defined alerts from the central lab. The Investigator will review the lab alerts and assess clinical significance for potential adverse events.

Blood samples for biomarker, exploratory research, and Pharmacokinetic (PK) analysis will be collected and processed as indicated in Section 5.3.1.2 and Section 5.3.2 (PK). Samples will be shipped to the Central Laboratory by the Study Site and then shipped by the Central Laboratory to AbbVie for analysis.

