## 9.4 Analysis of Vital Signs and Weights

Vital sign measurements of pulse rate, sitting systolic blood pressure, and sitting diastolic blood pressure will be summarized.

Each vital sign variable and weight will be summarized for all time points (starting with Baseline) with the number of non-missing observations, mean and standard deviation, median, minimum and maximum. Mean change from baseline to each applicable post-baseline visit will be summarized for each vital sign variable, with the number of observations, baseline mean, and visit mean. The change from baseline mean, standard error, and 95% confidence interval will be presented for the mean change from baseline within each treatment group and difference between elagolix group and placebo.

The number and percentage of subjects who have potentially clinically significant (PCS) vital sign and weight values meeting the following criteria will be summarized by treatment group. All increase/decrease is calculated from Baseline to a post-baseline visit in the Treatment Period.

- Diastolic blood pressure
  - $\circ \leq 50 \text{ mmHg and} \geq 15 \text{ mmHg decrease}$
  - $\circ$  > 90 mmHg and  $\geq$  15 mmHg increase
  - $\circ \geq 100 \text{ mmHg}$
- Systolic blood pressure
  - $\circ \leq 90 \text{ mmHg and} \geq 20 \text{ mmHg decrease}$

- $\circ \geq 140 \text{ mmHg and} \geq 20 \text{ mmHg increase}$
- $\circ \geq 160 \text{ mmHg}$
- Pulse rate
  - $\circ \leq 45$  bpm and  $\geq 15$  bpm decrease
  - $\circ$  > 100 bpm and  $\geq$  15 bpm increase
  - $\circ ~~ \geq 120 ~bpm$
- Weight
  - $\circ \geq 5\%$  decrease
  - $\circ \geq 7\%$  increase.

Listings will be provided to summarize subject-level vital sign and weight data for subjects meeting PCS criteria.

The number and percentage of subjects who had a sustained PCS vital sign and weight values will be summarized by treatment group and a listing of these subjects will be provided. A sustained PCS value is defined as 3 consecutive PCS values.

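### The any-time lipid counts in SAP 9.3 ignore baseline, so they mix pre-existing with new abnormality; an added row for women at risk would separate the two.

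*SAP*

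**What the plan says.** SAP 9.3 (Analysis of Laboratory Data) plans, by treatment group, the number and percentage of women "who have potentially clinically significant (PCS) lipid values meeting the following criteria any time during the appropriate Treatment Period". The seven criteria are fixed values: "Total cholesterol > 200 mg/dL", LDL-C above 130 and above 160, HDL-C below 40, triglycerides above 150, TG/HDL-C above 3.5 and LDL-C/HDL-C above 4. None refers to baseline.

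The neighbouring rules do take a position on baseline:

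- For ALT, AST and bilirubin, SAP 9.3 says that "the post-baseline laboratory value does not need to be worse than Baseline laboratory value", so baseline is expressly ignored.
- For vital signs and weight, SAP 9.4 builds a change into most criteria: "All increase/decrease is calculated from Baseline to a post-baseline visit in the Treatment Period".
- For the lipid criteria, neither rule is written.

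Entry does not keep out women who are already over a cut-off. The relevant exclusion in protocol 5.2.2 is a matter of judgement ("Subject has clinically significant abnormalities in clinical chemistry, hematology, or urinalysis") and sets no numeric lipid limit. On timing, the protocol's Clinical Laboratory Tests section states: "The laboratory test results obtained from the Day 1 pre-dose samples will serve as the baseline for clinical assessment". Protocol 5.1 starts the Treatment Period on Day 1, so the pre-dose sample is not clearly excluded from the any-time window.

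**The concern.** Lipid abnormality is an event of special interest (protocol 6.1.1.3; SAP Appendix A). Protocol 3.2.2 reports mean rises in total cholesterol, HDL-C, LDL-C and triglycerides on elagolix in Phase 2, only partly offset by E2/NETA. A reader will look to these counts for how many women developed an abnormal value on treatment.

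A woman above 200 mg/dL before her first dose who stays there is counted in whichever arm she is in. In Year 1 such women add to both arms and shrink the contrast. In the open-label and All Elagolix summaries there is no placebo column from which to judge how much of the count was there already.

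**Working it through.** The plan states no rate, prevalence or power for these counts, so there is no figure to reproduce. All prevalences, means, SDs and drug effects below are assumptions.

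**1. Which planned outputs give baseline status at the same cut-off?** (SAP 9.3)

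| Criterion | Baseline and by-visit bands | Worst-versus-baseline plot |
|---|---|---|
| Total cholesterol > 200 | none; lowest cut is 300 | no |
| LDL-C > 130, > 160 | yes, apart from values exactly at the cut | yes |
| HDL-C < 40 | yes | yes |
| TG > 150 | yes | yes |
| TG/HDL-C > 3.5 | no band | no |
| LDL-C/HDL-C > 4 | none; the cut is 3 | no |

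Four of the seven criteria have a baseline count and three do not. For the four, the baseline count is a separate total. No planned table crosses baseline status with the any-time count. The listing of women meeting the criteria omits women who never meet them, so it does not give the number at risk.

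**2. Direction of the effect.** Let a share b be over the cut-off at baseline in both arms and remain over it, and let q be the proportion of the others who cross. Then p = b + (1 − b)q, and the risk difference is (1 − b)(q1 − q0). Take q0 = 10% and q1 = 20%, so that the difference among women at risk is 10 points and the ratio is 2.00.

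- b = 20%: 28% v 36%, difference 8 points, ratio 1.29
- b = 30%: 37% v 44%, difference 7 points, ratio 1.19
- b = 40%: 46% v 52%, difference 6 points, ratio 1.13

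**3. Size for total cholesterol > 200 in Year 1.** I simulated 400,000 women per arm, each with one baseline and four post-baseline values (lipid panels at Months 3, 6, 9 and 12, protocol Appendix C). Between-woman SD was 32 and within-woman SD 14.

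| Mean, drug effect (mg/dL) | Over 200 at baseline | Planned count, placebo v elagolix | Ratio; difference | At risk, placebo v elagolix | Ratio; difference |
|---|---|---|---|---|---|
| 180, +5 | 28% | 43.3% v 49.3% | 1.14; 6.0 | 24.0% v 31.1% | 1.30; 7.1 |
| 180, +15 | 28% | 43.3% v 61.0% | 1.41; 17.7 | 24.0% v 46.1% | 1.92; 22.1 |
| 185, +10 | 33% | 49.1% v 61.0% | 1.24; 11.9 | 27.1% v 42.5% | 1.57; 15.4 |
| 190, +5 | 39% | 55.3% v 61.0% | 1.10; 5.8 | 30.6% v 38.4% | 1.25; 7.8 |
| 190, +15 | 39% | 55.3% v 71.9% | 1.30; 16.6 | 30.5% v 54.5% | 1.79; 24.0 |

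Of placebo women above 200 at baseline, 92-94% are counted again with no drug effect. Of elagolix women counted, 46-62% were already above at baseline.

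**4. Open label.** With 12 post-baseline panels (every three months from Month 15 to Month 48) and the same drug effects, 40-55% of women counted were above 200 before their first dose of elagolix. With the drug effect set to zero, 36-44% of women at or below 200 at baseline still cross it at least once, through within-woman variation alone.

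**5. HDL-C < 40.** The drug may raise HDL-C, so some women below 40 at baseline can leave the count and the formula in step 2 no longer holds. With an assumed mean of 55, SDs of 13 and 5, and a drug effect of +3 mg/dL, the planned count is 23.2% v 16.9% (difference −6.3 points, ratio 0.73). Among women at or above 40 at baseline it is 12.3% v 6.8% (−5.5 points, ratio 0.55). The ratio is diluted; the difference is not.

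**The case against.** The strongest reply is that these counts are not the plan's main lipid contrast. SAP 9.3 gives mean change from baseline at each visit, within arm and as a difference from placebo with a 95% CI, for all lipid variables including total cholesterol and the ratios. Pre-existing elevation does not dilute that analysis. Shift tables ("Changes in selected laboratory parameters will be tabulated using shift tables by NCI CTC criteria", or by normal range) and the worst-versus-baseline plots also use baseline. Absolute cut-offs are ordinary in this SAP: the liver criteria ignore baseline, and SAP 9.4 has absolute-only limits such as systolic pressure of 160 mmHg or more. The lipid counts are descriptive, with no named test and no planned ratio. On the difference scale, with a small drug effect, the loss is about 6 points against 7-8. All of this stands, and it makes the point a modest one. It does not supply a count of new cases.

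Three stronger readings should be resisted.

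- A reader might infer that Year 1 is biased towards one arm. Randomisation balances baseline prevalence in expectation, so the effect is attenuation.
- A reader might infer that pre-existing cases are why the open-label counts cannot be attributed to drug, and that a baseline condition would cure this. The reason is the absence of a concurrent control. Step 4 shows many women crossing with no drug effect at all, so the at-risk row would not establish attribution either.
- A reader might infer that the shift tables certainly use other cut-offs. The documents do not give the laboratory's normal ranges for lipids, so a range that ends at 200 mg/dL cannot be ruled out.

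**Conclusion.** The point holds as a limited one. The any-time lipid counts measure the proportion ever over a cut-off, not the proportion newly over it, and no planned table separates the two. For criteria that the drug worsens, the Year 1 contrast is attenuated. For HDL-C < 40 the ratio is diluted but the difference need not be. In the open-label and All Elagolix summaries the apparent number of new cases is inflated. The gap is widest for total cholesterol > 200, TG/HDL-C > 3.5 and LDL-C/HDL-C > 4, which have no baseline count at all.

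Under the assumptions in step 3, the Year 1 ratio for total cholesterol is about 1.1-1.4 as planned against 1.3-1.9 among women at risk, and the difference is about 6-18 against 7-24 points. Only total cholesterol and HDL-C were modelled, and every input is assumed, so the true size is unknown. The planned mean-change comparison is unaffected.

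**What to change.** In SAP 9.3:

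1. Keep the planned any-time count, and state that only values after the baseline for that analysis set qualify.
2. For each criterion, and at minimum the three without a baseline counterpart, add n/N among women who did not meet it at the baseline that SAP 9.1 defines for that analysis set. Show women who already met it on a separate row.
3. Footnote the open-label and All Elagolix tables to say that the at-risk row separates new from pre-existing cases but does not establish attribution to drug, because there is no concurrent control.

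This uses data already collected and takes a sentence and two rows per criterion. The cost is a smaller denominator. In the case with mean 185 and effect +10, using the SAP's 167 and 333 women, about 111 and 222 remain. The standard error of the difference, √[p0(1 − p0)/n0 + p1(1 − p1)/n1], rises from 4.7 to 5.4 points, while the difference itself rises from 11.9 to 15.4 points.

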- (unless known diagnosis of Gilbert's disease)  $\geq 2.0$  times the upper limit of the reference range.
- 12. Subject has a reactive or positive Screening test result for Hepatitis A Virus Immunoglobulin M (HAV IgM), Hepatitis B Surface Antigen (HBsAg) or Hepatitis C Virus Antibody (HCV Ab) or Human Immunodeficiency Virus (HIV) or HIV Antibody (HIV Ab).
- 13. Subject has clinically significant abnormal ECG.
- 14. Subject is less than 6 months post-partum, post-abortion, post-pregnancy, or post lactation at the time of entry into the Screening Period, is pregnant or breastfeeding or is planning a pregnancy within the next 48 months.
- 15. Subject was diagnosed with a hereditary blood coagulation disorder (e.g., Von Willebrand disease, Factor V Leiden), or has a history of surgery-related severe bleeding or severe and prolonged bleeding associated with dental work.
- 16. Subject has a history of osteoporosis or other metabolic bone disease, including:
  - Screening DXA results of the lumbar spine (L1 L4), femoral neck, or total hip BMD corresponding to 2.0 or more standard deviations below normal (T-score  $\leq$  –2.0)
  - Intercurrent bone disease (e.g., osteomalacia, osteogenesis imperfecta, etc.)
  - Condition that would interfere with obtaining adequate DXA measurements (e.g., history of spinal surgery, spinal hardware or severe scoliosis).
  - History or presence of a condition that is associated with a decrease in BMD (e.g., uncontrolled hyperthyroidism, uncontrolled hyperparathyroidism, anorexia nervosa) or requires chronic treatment with systemic corticosteroids.
  - History of low-trauma bone fractures (e.g., fracture resulting from a fall from a standing height or lower)
  - Bilateral hip replacement
  - Clinically significant hypocalcemia, hypo- or hyperphosphatemia
  - Treatment with medication (excluding calcium and vitamin D) for bone disease associated with a decrease in BMD

- 17. Subject has a history of major depression or post-traumatic stress disorder (PTSD) episode within 2 years of Screening, OR a history of other major psychiatric disorder at any time (e.g., schizophrenia, bipolar disorder).
- 18. Subject has a history of suicide attempts or answered "yes" to questions 4 or 5 on the suicidal ideation portion of the Columbia-Suicide Severity Rating Scale (C-SSRS) within the last 1 year at Screening or Day 1, prior to randomization.
- 19. Subject has either:

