# 5.4 Removal of Subjects from Therapy or Assessment

Each subject has the right to withdraw from the study at any time. In addition, the Investigator may discontinue a subject from the study at any time if the Investigator considers it necessary for any reason, including the occurrence of an adverse event or noncompliance with the protocol. Subjects who withdraw from the study will not be replaced unless it is mutually agreed upon, in writing, by the Investigator and AbbVie. Each subject will be withdrawn from the study if any of the following occur:

- The subject decides to withdraw consent for any reason.
- The investigator believes it is in the best interest of the subject.
- Clinically significant deterioration of the subject's medical status as determined by the investigator.
- The subject requires surgical intervention for treatment of uterine fibroids and menstrual bleeding or other procedures including hysterectomy, myomectomy, uterine artery embolization, high intensity focused ultrasound (HIFU), endometrial ablation, dilation and curettage (D&C), etc. during the Treatment Period. In the Post-Treatment Follow-Up Period these procedures do not

warrant withdrawal if performed during the Post-Treatment Follow-Up Period unless a hysterectomy with bilateral salpingo-oophorectomy (BSO) is performed in the Post-Treatment Follow-Up Period and the subject does not plan to use Hormone Replacement Therapy within 1 month of the surgery date.

- The subject becomes pregnant or has a positive serum pregnancy test.
- The subject has SGPT/ALAT or SGOT/ASAT elevation > 5 times the upper limit of normal, confirmed upon repeat testing during the Treatment Period.
- The subject develops clinically significant gynecological findings or condition on either the TAU/TVU (confirmed by repeat TAU/TVU and/or SIS and/or office hysteroscopy) or endometrial biopsy that in the opinion of the Investigator or AbbVie TA MD would preclude the subject from continuing in the Treatment Period due to safety reasons.
- The results of any post-baseline DXA prior to Month 48 document a T-score < -2.5 in the lumbar spine, total hip or femoral neck, a BMD decrease of > 8% in the lumbar spine, total hip, or femoral neck, or due to TA MD assessment when the BMD percent change from baseline cannot be provided by the central reader.

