### Study Activities – Post-Treatment Follow-Up Period

	Pos	t-Treatment Follow-	U p a
	Month 1	Month 6	Month 12
On-site Visit	X		
Phone Visit		X	X
Physical Examination	X b		
Return to Menses Questionnaire c	X	X	
DXA Scan d		X	X
Pregnancy Test e	X (u, s)	$X^{f}(u)$	Xf (u)
Urine (u), serum (s)			
Serum Estradiol (E2) and FSH sample	X		
Lipid Panel and Subset of Chemistry Labs: ALT, AST, Bilirubin and Alkaline Phosphatase	X		
Review Adverse Events	$X^g$		
Review Adverse Events of Special Interest (Bone) h		X	X
Review Concomitant Medication	X	X	X

- a. Refer to Table 1 Visit and Assessment Windows, for allowable visit and assessment-specific windows during the Post-Treatment Follow-Up Period.
- b. Brief, symptom-directed examination to assess any ongoing AEs for resolution.
- c. If the subject has a documented menstrual period after the last dose of study drug, the subject may begin the use of hormonal contraception (e.g., oral or IUD) in place of non hormonal birth control.
- d. Site staff to contact subjects to ensure Month 6 and 12 DXA scans are scheduled within the visit window (refer to Table 1).
- e. A positive urine pregnancy test result must be confirmed with a serum pregnancy test. For any subject who has a positive serum pregnancy test result during the Post-Treatment Follow-Up Period, a TVU must be conducted as early as possible in the first trimester in order to assess the conception date. The subject will be discontinued from the Post-Treatment Follow-Up Period at the point the pregnancy is confirmed.
- f. A negative urine pregnancy test must be obtained within 2 days prior to performing the DXA. A positive urine pregnancy test result must be confirmed with a serum pregnancy test. For any subject who has a positive serum pregnancy test result, the DXA should not be performed. The subject will be discontinued from the Follow-Up Period at the point the pregnancy is confirmed.
- g. Any ongoing adverse events at the end of the Treatment Period will be reviewed for resolution during this visit.
- h. AESIs of bone fracture, clinically significant BMD loss, or newly diagnosed medically-related bone condition will be collected during the Post-Treatment Follow-Up Period.

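### The combined liver rows stop at on-treatment values, with that window undefined, and have no time-linked row beside them, so a bilirubin rise after the last dose is tabulated as bilirubin below 2 × ULN

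*SAP*

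**What the plan says.** SAP 9.3 tabulates, by treatment group, women "with maximum on treatment laboratory values meeting the following criteria compared to the upper limit of normal (ULN) during the appropriate Treatment Period", and says that these counts "will be summarized to assess potential hepatotoxicity". The combined rows cross ALT, AST or both at or above 3 × ULN with total bilirubin at or above 2 × ULN, below 2 × ULN, or at or above 1.5 × ULN.

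Three rules govern the rows:

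- Each analyte enters through its own highest multiple of the ULN.
- On timing, the SAP states: "The ALT, AST, and total bilirubin values do not need to be concurrent in order to meet the defined criteria".
- A value counts whether or not it is worse than baseline.

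A listing of all ALT, AST, bilirubin and alkaline phosphatase values is planned for every woman who meets any criterion. Plots of peak ALT and peak AST against peak bilirubin are also planned.

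The protocol bears on the rows in three places:

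- Section 5.4 lists as a reason for withdrawal: "The subject has SGPT/ALAT or SGOT/ASAT elevation > 5 times the upper limit of normal, confirmed upon repeat testing during the Treatment Period".
- The post-treatment schedule in Appendix C includes, at Follow-Up Month 1, "Lipid Panel and Subset of Chemistry Labs: ALT, AST, Bilirubin and Alkaline Phosphatase".
- Exclusion criterion 11 in Section 5.2.2 bars bilirubin at or above 2 × ULN "unless known diagnosis of Gilbert's disease".

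**The concern.** There are two separate matters.

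The first is the window. Enzymes and bilirubin need not peak together. If bilirubin rises after the drug is stopped, the sample that shows it may be the one drawn at Follow-Up Month 1, which the rows do not use. The woman then appears in the more reassuring of two adjacent rows. Women withdrawn for confirmed enzyme elevation are among those who could be affected.

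The second is the lack of a time link. Two maxima from one woman can come from unrelated episodes. The longer the treatment, the more room there is for that, and the long summaries have no concurrent placebo group to show the background.

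Counts of combined elevation are normally small, so moving one woman between rows can change how a table in a study of about 500 women is read.

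**Working it through.** **1. The window.** The relevant provisions, side by side:

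| Item | Source | Window after last dose |
|---|---|---|
| Liver rows | SAP 9.3 | On-treatment maxima; later text says during the Treatment Period; no lag given |
| Treatment-emergent adverse events | SAP 9.2.1 | Up to 30 days |
| Exposure for event rates | SAP 9.2.4 | Last dose minus first dose plus 30 days |
| Premature Discontinuation sample | Protocol 5.4.1, Appendix C | Preferably 2–7 days; full chemistry |
| Follow-Up Month 1 sample | Protocol Appendix C, Table 1 | Nominally 28 days, ± 7 days |

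With a 28-day month, Follow-Up Month 1 falls at 28 − 7 = 21 to 28 + 7 = 35 days after the last dose. At the nominal day 28, a hepatic adverse event is treatment-emergent, while a bilirubin result from the same visit is outside the liver rows. Whether the Premature Discontinuation sample counts is unclear: it sits in the Treatment Period schedule but is drawn after the last dose.

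Take a woman with ALT at or above 3 × ULN on drug, all on-treatment bilirubin values below 2 × ULN, and bilirubin at or above 2 × ULN first seen at Follow-Up Month 1. Her on-treatment bilirubin maximum is below 2 × ULN, so she is counted in that row and not in the combined row.

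**2. How far apart paired peaks can be.** First, the plan's own durations: 12 × 28 = 336, 36 × 28 = 1008 and 48 × 28 = 1344 days. These match the top duration intervals in SAP 6.0. Appendix C schedules liver tests every 3 months on treatment.

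| Summary | First to last scheduled test | Largest gap | Tests |
|---|---|---|---|
| Placebo-controlled | Month 3 to 12 | 9 × 28 = 252 days (0.69 years) | 4 |
| Open-label | Month 15 to 48 | 33 × 28 = 924 days (2.53 years) | 12 |
| All Elagolix | Month 3 to 48 | 45 × 28 = 1260 days (3.45 years) | 16 |

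If two unrelated peaks fall uniformly over 16 visits, they share a visit with probability 1/16 = 6% and lie within one visit of each other with probability (16 + 2 × 15)/16² = 18%.

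**3. Chance pairing, on assumed rates.** The documents give no rates. Suppose an unrelated bilirubin at or above 2 × ULN occurs at any visit with probability p of 0.1% to 1%, independently between visits. Given an ALT peak, the chance of a pairing is 1 − (1 − p)^k:

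- k = 4: 0.4% to 3.9%
- k = 12: 1.2% to 11.4%
- k = 16: 1.6% to 14.9%

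The 16-visit figure applies to few women, because the sample-size section expects about 30 to receive 48 months of active drug. If 1% of those 30 have an ALT peak, the expected number of chance pairs is 30 × 0.01 × (0.016 to 0.149) = about 0.005 to 0.045.

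A second illustration takes 500 women, with independent per-woman rates for an ALT peak and for a bilirubin peak:

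- At 1% each, 500 × 0.01 × 0.01 = 0.05 pairs are expected, and the chance of at least one is 1 − (1 − 0.0001)^500 = 4.9%.
- At 3% each, 500 × 0.03 × 0.03 = 0.45 pairs are expected, and the chance is 1 − (1 − 0.0009)^500 = 36%.

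**The case against.** The strongest reply is that the rows are a declared screen. The SAP states openly that the values need not coincide or exceed baseline, and it speaks only of potential hepatotoxicity. The counts equal their definition. That stands, and the rows should stay.

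A reader might infer that the rule both manufactures and conceals liver-injury cases. The documents do not support this, for four reasons:

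- Gaps of years cannot arise in the randomised comparison, where the limit between scheduled tests is 252 days.
- The larger chance figures are conditional on an ALT peak, rest on assumed rates and concern few women. Bilirubin elevations probably cluster within women, which would lower them further.
- A woman with known Gilbert's disease and bilirubin persistently at or above 2 × ULN would also meet a same-day rule. Her inclusion comes from disregarding baseline, not from pairing peaks at different times.
- A late bilirubin rise need not be lost to the report. Her ALT puts her in the listing, laboratory variables are summarised at all time points, and hepatic events are searched as events of special interest (SAP Appendix A). Protocol 5.4.1 also provides follow-up of clinically significant results unresolved at discontinuation.

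What remains is narrower. The listing does not alter the counts by group, and the SAP does not say that it includes follow-up values. The screen also cannot detect bilirubin that rises after its window closes.

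**Conclusion.** The point holds in limited form, as a cheap improvement. On the plain reading of SAP 9.3, a bilirubin rise first seen at Follow-Up Month 1 leaves the woman in the row for bilirubin below 2 × ULN, although the SAP's adverse-event window runs to 30 days. This follows from the text and needs no assumed rate; how many women it affects cannot be derived from the documents.

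For the pairing of peaks, the conclusion is only that the open-label and All Elagolix counts cannot separate related from unrelated elevations without a time-linked row. The expected number of chance pairs is below one under every assumption shown above. Both effects are confined to the tabulated counts and the peak-versus-peak plots.

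**What to change.** In SAP 9.3:

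1. Define the laboratory window for the liver rows and plots as first dose in the relevant analysis through the Follow-Up Month 1 sample, explicitly including the Premature Discontinuation sample. For women who continue, end the placebo-controlled window at the first open-label dose.
2. Keep the existing rows as a screen. Add rows requiring total bilirubin at or above 2 × ULN, and at or above 1.5 × ULN, on the same day as or within 30 days after ALT or AST at or above 3 × ULN. The 30 days is a choice that mirrors the adverse-event window; the documents give no laboratory equivalent.
3. Flag women with known Gilbert's disease or baseline bilirubin at or above 2 × ULN.

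The cost is SAP wording and a few table rows. The samples are already scheduled, and no clinical rule changes. One limit should be stated: scheduled tests are 3 × 28 = 84 days apart, so the time-linked rows will rest mostly on same-sample, repeat, discontinuation and follow-up draws. They supplement the screen and cannot replace it.
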